3.3 Exploratory Objective

Explore whether of 0.5% bupivacaine with 1:200,000 epinephrine provides pulpal anesthesia success and onset which is not different from 2% lidocaine with 1:100,000 epinephrine.

4 Study Endpoints

4.1.1 Primary Study Endpoints

Oral health related quality of life OHIP-14 score changes from preoperative to postoperatively day 1 and day 5.

4.1.2 Secondary Study Endpoints

- Postoperative pain intensity during 5 days
- Number and type of pain medication use
- Duration of LA in hours (numbness) after receiving pulpectomy/endodontic debridement

4.1.3 Exploratory Endpoints

- Cold test results (+/-)
- Number of supplemental injections
- Duration until adequate lip numbness is obtained (in minutes)
- Duration until negative cold response is obtained (in minutes)

CONFIDENTIAL

This material is the property of the NYU School of Medicine and Langone Medical Center. Do not disclose or use except as authorized in writing by the study sponsor

5 Study Enrollment and Withdrawal.

5.1 Inclusion Criteria

In order to be eligible to participate in this study, an individual must meet all of the following criteria:

1. Patients between the ages of 18-85 years old.
2. Patients with pulpal diagnosis of either symptomatic irreversible pulpitis or pulp necrosis and periapical diagnosis of normal apical tissues, symptomatic apical periodontitis or asymptomatic apical periodontitis.
3. Patients who only have one tooth with odontogenic pain at the time point of the screening.
4. Patients who are treatment planned, and have agreed to have, pulpectomy/endodontic debridement.
5. Patients with acute dental pain of at least 3/10 on NRS.
6. Patients must be able to comprehend and complete all study questionnaires.
7. Patients must be able to comprehend the description of the study protocol and written consent.
8. Patients must be available to be contacted by text messages, phone calls or email during 5 days after the pulpectomy/endodontic debridement.

5.2 Exclusion Criteria

An individual who meets any of the following criteria will be excluded from participation in this study:

1. Medically complex patients with severe systemic diseases (ASA III or above). These may include uncontrolled diabetes, uncontrolled blood pressure and/or chronic renal failure, for example, and potential participants will be asked about these conditions during the screening process.
2. Pregnant patients.
3. Patients who have already been enrolled in the study. Patients can only be enrolled for treatment on one tooth. If a patient has been enrolled in the study and will receive additional endodontic treatment on a different tooth on a later date, they will not be enrolled again for the additional endodontic treatment on a different tooth.
4. Patients with a known hypersensitivity or allergy to any local anesthetic agent of the amide group, or any other components of the two anesthetic solutions such as epinephrine, sodium metabisulfite used in the study.
5. Patients who use ergot-type oxytocic drugs for uterine contraction, monoamine oxidase inhibitors, antidepressant of triptyline or imipramine types or patients who are planned to receive sedatives for the treatment.
6. Patients with additional elective dental treatments like extraction, implant placement, root canal therapy planned in the 5 days following the date of enrollment in this study.
7. Patients with pain whose examined tooth is planned for vital pulp therapies e.g. pulpotomy, retreatment, apical surgery or extraction.
8. Patients with a pulpal diagnosis of reversible pulpitis, previously treated, previously initiated therapy and periapical diagnosis of acute apical abscess or chronic apical abscess.
9. Patients who have multiple teeth with odontogenic pain at the time of the screening.
10. Patients who do not understand or are able to read the questionnaires.
11. Non-English speaking patients.

5.3 Intraoperative Exclusion criteria

An individual who meets any of the following criteria will be excluded from participation in this study:

1. Patients, whose endodontic treatment cannot be continued due to intra-procedural findings such as tooth fracture.
2. Any unexpected intraoperative procedural errors that might change the course of the treatment, such as separated instrument, perforation.
3. Patients whose adequate lip numbness is not obtained with 2 inferior alveolar nerve blocks.

CONFIDENTIAL

This material is the property of the NYU School of Medicine and Langone Medical Center. Do not disclose or use except as authorized in writing by the study sponsor

4. Patients whose adequate pulpal anesthesia is not obtained after 2 supplemental injections of anesthetic.

5.4 Vulnerable Subjects

No vulnerable patients will be specifically targeted for inclusion in this study.

5.5 Strategies for Recruitment and Retention

Patients recruited in this study will be mostly those who present for emergency dental treatment at NYU Dentistry Endodontic Clinic. The dental providers are postgraduate students from the endodontic department and they work under the supervision of the NYS Dental Licensed faculty, listed as Co-Investigators, who will be overseeing the procedures and treatments which are part of the study. Study investigators (the PI, Co-PIs;) will identify patients who need an emergency treatment either by inquiring directly to the dental providers at the start of the clinic session and through the day or by asking the front desk patient representatives in the Endodontic clinic if any emergency patients presented on that day. It is also possible that some patients who come for a treatment appointment might have a symptomatic tooth.

The potential participant's standard of care clinical and radiographic examination findings, diagnosis and treatment plan approved by the faculty will be prescreened by one of the study investigators after the standard of care clinical and radiographic examinations performed by the treating dentist to determine whether the patient is eligible in terms of diagnosis and treatment plan approved by the faculty by reviewing the gathered findings. This will be done in an effort to not to increase the wait time period for patients. After prescreening, potential participant will be asked by their dental provider if they are interested in discussing participation in a research study regarding postoperative pain with a research investigator. Interested subjects will be introduced to the study – this means the purpose of the study will be explained, details of what will be involved if they decide to participate will be described, duration of the study etc. by the PI or the Co-I; [name]. If they agree to participate, they will be consented by the PI or the Co-I; [name].

Interested potential subjects will be screened for eligibility by one of the study investigators and will be enrolled if they meet all the eligibility criteria.

We estimate 80 subjects (randomized to 40 participants per arm) are required. We estimate that loss of subjects will be minimal due to a short follow up time of 1 week, however in order to anticipate a greater loss of subjects because of intraoperative exclusion criteria, we will increase our sample size to 100 to include 20% attrition (n=50 per treatment group).

We are unsure of how many cases will be screened in order to reach this approximate sample size but we will update the protocol as this information is obtained.

5.6 Duration of Study Participation

The duration of study participation will be from the 1st treatment visit, until the participant returns for their second routine endodontic treatment visit. At this second visit, compensation will be given and data collection will be finalized if necessary. This is in an effort to coincide the research visit with the routine and required dental visit. This visit will be scheduled by the treating dentist and can be scheduled up to several weeks after the first treatment visit. There will be no time limit for this research visit. If the patient will return to the school for an appointment in another department/clinic, they can inform the research team and efforts will be made to meet the patient then if the 5 days post-treatment data collection is complete.

5.7 Total Number of Participants

Recruitment will end when approximately 100 evaluable participants are enrolled, randomized to 50 subjects per group.

CONFIDENTIAL

5.8 Participant Withdrawal or Termination

5.8.1 Reasons for Withdrawal or Termination

Participants are free to withdraw from participation in the study at any time upon request. An investigator may terminate participation in the study if:

- Any clinical adverse event (AE), or other medical/dental condition or situation occurs such that continued participation in the study would not be in the best interest of the participant.
- The participant meets an exclusion criterion (either newly developed or not previously recognized) that precludes further study participation – this may include intra-operative factors outlined in the Intraoperative Exclusion Criteria including: fracture of the tooth, not having adequate lip numbness after 2nd inferior alveolar nerve block, or not having adequate pulpal anesthesia after two times supplemental injection.
- Failure of the subject to adhere to protocol requirements such as not completing the remote questionnaires after the treatment.

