5.8.2 Handling of Participant Withdrawals or Termination

Efforts will be made prior to stating that a participant is lost to follow up (LTF) by contacting the participant with the contact information provided pre-operatively either by phone/text/email. We will also obtain a friend/family member's contact information to contact the subject in order to avoid LTF.

If the IANB fails to provide adequate lip numbness after the second injection and after a wait time of a further 15 minutes (total wait time 30 minutes), the subject will discontinue with the study agent/control agent, and will be excluded from the study. Also, subjects who need supplemental injections more than 2 times will be excluded from the study. The treating dentist will be unblinded and routine protocol will be followed; Lidocaine 2% with 1:100,000 epinephrine will be administered either with an IANB, infiltration or intraosseous anesthesia as decided by the treating dentist. Every failure for these reasons will be noted by the researchers and analyzed at later time to investigate possible difference in success of each of the two LA.

The study team will try to determine reasons for discontinuation and a subject disposition document will be completed to record reason for discontinuation. Subjects who decide to discontinue participation from the study will be provided with contact information of the PI and the study team if any questions or concerns arise at a later point. If the subject would like written confirmation of their discontinuation, a withdrawal letter will be given to them, signed by the PI. It will not be required for subjects to return to the clinic for any safety follow-up visits.

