After the adequate lip numbness is gained, another 10 minutes will be waited to achieve pulpal anesthesia; Cold Test – As per standard of care, Endo-Ice (Coltene, USA) will be administered to subjects to determine the success of pulpal This is a routine step in endodontic treatment. A cotton pellet is sprayed with the refrigerant spray and applied the tooth. A painful response will indicate inadequate pulpal anesthesia.

Subjects in each group will also receive a buccal infiltration and IL injection with Lidocaine which is highly recommended for symptomatic teeth. The Cold Test will be repeated to determine anesthesia. The algorithmic chart for anesthetic administration in the supplementary form *Pulpectomy/Endodontic Debridement Method* will be followed as the guideline. Additional supplemental injections will be administered as portrayed in the chart with Lidocaine HCl 2% 1:100,00 in both groups if needed, until pulpal anesthesia is obtained to initiate treatment, without jeopardizing the maximum dose limit for the subject.

Subjects who need supplemental injections more than 2 times will be excluded the study.

4. Intra- and Immediate Post-operative Data Collection:

- Pre-operative data obtained after clinical and radiographic examination which are performed as standard of care, before the treatment procedure, such as cold test response, percussion hypersensitivity, pulpal and periapical diagnosis will be collected by a study investigator by the end of the treatment, together with the intraoperative and immediate postoperative data.
- Intraoperative data such as number of cartridges used, time for adequate anesthesia, additional supplementary anesthesia will be collected.
- Intraoperative pain will be evaluated on a NRS by asking the subject directly after treatment.

5. Remote Data Collection:

Subjects will receive surveys remotely either by e-mail through REDCap, which will ask about their pain intensity reported on an NRS, analgesic medication use and numbness. REDCap surveys will be sent at 6, 12, 24, 48, 72, 96 and 120 hours after treatment. On day 1 and 5, subjects will be assessed by OHIP14.

If subjects do not have access to the Internet, a study team member will call them. Paper questionnaires will also be an option if no other methods are convenient for subjects. If they prefer to fill in the questions and questionnaire on paper, they will be asked to bring them to their second appointment.

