10.1 Sample Size Determination

Based on a previous study, the mean change of overall OHIP-14 scores from baseline at 1 month follow up is 6 with a standard deviation of 13.3 (27). Assuming the mean change from preoperative baseline at day 1 and day 5 postoperatively in the lidocaine group is 6 and the standard deviation is 13.3 and assuming the standard deviation of the change from baseline at day 1 and day 5 postoperatively is the same in the bupivacaine group, then with 40 subjects in each of the 2 groups there is 80% power to detect a difference in the change from preoperative baseline of +/-9.3 between the 2 groups. Assuming significance level of 2.5% using a 2-sided 2-sample t-test (assuming the data are Normally distributed). The testing is done at 2.5% because the null hypothesis will be rejected if at least one of the changes, either from baseline to day 1 postoperatively or from baseline to day 5 postoperatively, is significantly different between the 2 groups.

Considering the dropout rate after randomization will be 20%, the total number of subjects need to be enrolled is 100. The dropped-out subjects are those who are needed to be excluded because of intraoperative exclusion criteria, and who are not compliant to complete postoperative questionnaires. NYU Dentistry, endodontic clinic is a busy clinic. We will most of the time recruit subjects from the endodontic emergency care where on a daily basis, on average 5 patients are being treated. However, we are unsure of how many cases will be screened in order to reach this approximate sample size but we will update the protocol as this information is obtained.

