10.2 Statistical Analysis

10.2.1 Analysis Dataset

The analysis dataset for study and control group will include subjects who receive IANB either with the study agent Bupivacaine or the control agent Lidocaine for the pulpectomy/endodontic debridement of symptomatic mandibular molar teeth diagnosed with either symptomatic irreversible pulpitis or pulp necrosis and periapical diagnosis of normal periapical tissues, asymptomatic or symptomatic apical periodontitis. The dataset will consist of preoperative data (demographics, preoperative pain assessment, PCS, LOT-R), initial clinical examination (cold test, percussion hypersensitivity), diagnosis, intraoperative data, initial and follow up OHIP-14 scores and postoperative pain, medication use and numbness. All analyses will be intent-to-treat dataset that includes all randomized patients and will use the analysis dataset.

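### Section 5.8.1 allows a treated subject's participation to be ended for not completing remote questionnaires, with no threshold and no continued OHIP-14 collection, so an obtainable day 1 or day 5 primary outcome may be lost

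*Combined protocol and SAP*

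**What the plan says.** The primary endpoint (4.1.1) is "Oral health related quality of life OHIP-14 score changes from preoperative to postoperatively day 1 and day 5". Both follow-up scores come from the remote phase (7.1.1): "On day 1 and 5, subjects will be assessed by OHIP14". The same section schedules the shorter surveys on pain, analgesic use and numbness: "REDCap surveys will be sent at 6, 12, 24, 48, 72, 96 and 120 hours after treatment".

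Section 5.8.1 opens its list of reasons with "An investigator may terminate participation in the study if" and includes "Failure of the subject to adhere to protocol requirements such as not completing the remote questionnaires after the treatment". It does not say how many questionnaires must be missed, and it does not separate the short surveys from OHIP-14.

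Section 10.1 Sample Size Determination places in its 20% dropout figure, beside the intraoperative exclusions, subjects "who are not compliant to complete postoperative questionnaires".

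Section 5.8.2 deals with loss to follow-up: "Efforts will be made prior to stating that a participant is lost to follow up (LTF) by contacting the participant". Sections 5.8.2 and 7.2.5 also require the reason for discontinuation to be documented. None of these sections says that outcomes are still collected once participation has been terminated.

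Section 10.2.1 states: "All analyses will be intent-to-treat dataset that includes all randomized patients".

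**The concern.** The anaesthetic is given at one visit. Ending participation during the five remote days because a questionnaire was not completed stops no exposure to study drug. What it can stop is the collection of later outcomes, including the primary one, from someone who has been randomized and treated and may still be willing to answer.

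The timing makes this more than a bookkeeping matter. The Protocol Summary gives anaesthesia of up to 7 hours with bupivacaine and up to 4 hours with lidocaine, so the 6-hour survey falls where the arms are expected to differ. Non-response at 6 or 12 hours may plausibly be related to pain, analgesic use or numbness. If it is, ending participation turns an intermittent gap in a secondary measure into a permanent loss of the primary score, related to outcome and possibly to arm. The longitudinal mixed models of 10.2.4 can use subjects with gaps, so secondary data that could have been analysed may go as well.

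**Working it through.** **The plan's own sample size.** Inputs from 10.1: difference 9.3, SD 13.3, two-sided alpha 2.5%, power 80%, two-sample t-test, 20% dropout.

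- Normal approximation: n per arm = 2 × (2.2414 + 0.8416)² × (13.3 / 9.3)² = 2 × 9.505 × 2.045 = 38.9, so 39.
- Noncentral t: 40.2 per arm; power at 40 per arm is 79.8%; the detectable difference is 9.32.
- Inflation: 80 / (1 − 0.20) = 100.

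The stated 40 per arm and 100 in total reproduce. The sample size is not in dispute.

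**Can termination precede a primary outcome?** I take day 1 as 24 hours and day 5 as 120 hours; 7.1.1 gives no clock time for OHIP-14. The surveys at 6 and 12 hours then precede the day 1 score (2 surveys), and those at 6, 12, 24, 48, 72 and 96 hours precede the day 5 score (6 surveys). The ground in 5.8.1 can therefore arise while either score is still obtainable.

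**How many subjects could come within the rule?** The documents give no miss rate, so p is an assumption, taken as 3%, 5% and 10% per survey. On the widest reading (any one miss suffices) and with independent misses, the share is 1 − (1 − p)^k.

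| Assumed p | Before day 1 (k = 2) | Before day 5 (k = 6) |
|---|---|---|
| 3% | 1 − 0.97² = 5.9% | 1 − 0.97⁶ = 16.7% |
| 5% | 1 − 0.95² = 9.8% | 1 − 0.95⁶ = 26.5% |
| 10% | 1 − 0.90² = 19.0% | 1 − 0.90⁶ = 46.9% |

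Misses that cluster within subjects lower these shares. At the extreme where the same subjects miss every survey, the share is p itself: 3%, 5% or 10%. The table is therefore an upper bound on exposure under independent or positively clustered misses.

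**What retained outcomes are worth.** Power for a difference of 9.3 (t-test, two-sided 2.5%) by number of OHIP-14 outcomes per arm: 50 gives 88.7%, 45 gives 84.8%, 40 gives 79.8%, 36 gives 74.9%. Each treated subject kept moves the trial from the 40-per-arm floor towards 50.

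**The analysis side.** 10.2.1 promises all randomized patients. The test in 10.2.3 needs a change score, and no method is given there for a missing one. A subject terminated before day 5 thus belongs to the stated population but cannot enter the day 5 comparison. The dropout inflation in 10.1 protects power; it does nothing about bias if the loss is related to outcome.

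**The case against.** The strongest reply is that the rule is mild in practice. Termination is discretionary, and the plural wording may well mean a subject who leaves the questionnaires undone generally, not one who misses the 6-hour survey. Criterion 8 in 5.1 requires subjects to be reachable for the five days. Phone and paper routes exist (7.1.1). Paper forms come back at the second visit, so for those subjects non-completion would normally be seen only after day 5. Section 5.5 expects minimal loss to follow-up. All of this stands, and it lowers the likely number affected. None of it sets a threshold or keeps a terminated subject in OHIP-14 collection.

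Four stronger readings are tempting but not supported:

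- A reader might infer that 5.8.1 conflicts with 5.8.2. It does not: contact attempts come before a subject is declared lost, and 5.8.1 lists when participation may end. The two can operate in sequence.
- A reader might infer that surveys are the only study activity after treatment. Participation runs to the second visit (5.6, 7.2.4), unscheduled visits are documented (7.2.6), and adverse events are recorded to the last day of participation (8.3).
- A reader might set the 26% or 47% against the 20% dropout allowance and conclude that the allowance is exceeded. That treats everyone who could be terminated as terminated, contrary to the discretionary wording.
- A reader might infer that scores already collected from a terminated subject are discarded. No section says so.

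**Conclusion.** The point holds as a design weakness. A discretionary rule without a threshold can end outcome collection in treated subjects whose primary endpoint is still obtainable, and this works against the intent-to-treat statement. It is not an error of arithmetic.

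The exposure is at most about 6% to 19% of subjects before day 1 and 17% to 47% before day 5. This rests on assumed per-survey miss rates of 3% to 10%, independence between surveys, and the reading that one miss is enough. Actual losses would be smaller, and the documents do not allow them to be estimated. That the loss is related to pain, numbness or arm is plausible but not shown, so no size is put on the bias. The change is worth making because it is cheap and removes an avoidable loss, not because large loss is forecast.

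**What to change.** In 5.8.1, remove the questionnaire example and add text along these lines: *Missed questionnaires do not end participation. All remaining surveys and both OHIP-14 assessments continue to be sent through 120 hours, and a missed day 1 or day 5 OHIP-14 is pursued by telephone, unless the participant withdraws consent to further contact. All collected assessments are analysed.*

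In 10.1 Sample Size Determination, count as lost for the primary endpoint only subjects missing the relevant OHIP-14 score, so that a missed short survey is not read as dropout.

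The cost is a one-paragraph amendment and a matching edit in 10.1. The REDCap and telephone routes already exist in 7.1.1. The downside is a few more reminder calls. The planned sample size need not change.
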